COMIRB Protocol

COLORADO MULTIPLE INSTITUTIONAL REVIEW BOARD
[name] [contact] [contact]

Protocol #:15-2388

Project Title: Discontinuation of Disease Modifying Therapies (DMTs) in Multiple Sclerosis (MS)

Principal Investigator: [name]

Version Date: 10Jan2020

I. Hypotheses and Specific Aims:

Main hypothesis is that relatively older MS patients with no recent signs of new inflammatory disease activity (no relapses for at least five years and no new brain MRI lesions for at least three years) while on an approved MS DMT may safely discontinue DMTs from a medical perspective, ie no greater risk of new relapses or brain MRI scan changes due to MS, compared to those staying on their DMT. Secondary hypotheses are that in individual MS patients who discontinue DMTs in this context, there will be no significant increased risk of disease progression as measured by the EDSS, and no worsening of patient quality of life as measured by a series of Patient Reported Outcomes (PROs), compared to those staying on their DMT.

Specific Aims:

In MS patients 55 years of age or older, who have no evidence of new relapses for at least five years or brain MRI lesions for at least three years while continuously taking DMTs, we will compare clinically significant and patient-relevant outcomes in those who discontinue vs continue DMTs to determine if:

1. Risk of new relapses or brain MRI lesions is no worse in those discontinuing
2. Risk of disability progression (EDSS) is no worse in those discontinuing
3. Quality of life and other patient-reported outcomes (PROs) are no worse in those discontinuing

II. Background, Preliminary Studies, and Significance:

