 - ii. **SymptoMScreen (SymptoMScreen – overall symptom severity):** SymptoMScreen⁷⁹ is a rapid assessment tool that allows the patient to self-report across multiple neurological domains (mobility, hand function, spasticity, pain, sensory, bladder, fatigue, vision, dizziness, cognition, depression, and anxiety). This scale is a user friendly, single page validated measure that allows for quick assessment of multiple symptoms.
 - iii. **Patient Determined Disease Steps (PDDS – disability):** The Patient-Determined Disease Steps (PDDS) is a PRO version of the clinician-reported Extended Disability Status Scale (EDSS) which hones the stages of cane use and thus is more responsive to mid-range disability changes.⁷⁹ This tool asks the patient to characterize level of disability into one of nine steps (0=normal, 1=mild disability, 2=moderate disability, 3=gait disability, 4=early cane, 5=late cane, 6=bilateral support, 7=wheelchair scooter, 8=bedridden). The PDDS will be used to characterize (and to control for) disability in both study groups at all study time points.
 - iv. **The Symbol Digit Modalities Test (SDMT - cognition):** The SDMT measures patient attention, concentration, and speed of information processing and has been validated for discriminating patients from

controls even when it was administered each month over six months.⁸³ It is relatively simple to administer and only takes a few minutes to complete.

v. **Multiple Sclerosis Impact Scale (MSIS-29 – MS symptoms):** Since Neuro-QoL short form doesn't have the ability to provide an overall quality of life calculation, the study team added MSIS-29, which is an acceptable, reliable, and valid method for recording quality of life in MS patients.⁸⁰

vi. **Treatment Satisfaction Questions:** This was developed for qualitative and exploratory purposes. These questions will provide insight into patient satisfaction in regards to the disease modifying therapy (DMT) they are using at baseline, versus their ongoing satisfaction with their study care plan (on a DMT v. not on a DMT). The following question will be asked:

How satisfied are you with your current DMT (or lack of DMT)? Please circle one.

Very dissatisfied Dissatisfied Neutral Satisfied Very satisfied

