This will be a randomized discontinuation trial (RDT).⁷¹ While RDTs have been done in cancer^{72,73} and rheumatoid arthritis patients,⁶⁶ this would be the first such study in MS. Patients will be randomized to either continue with their present MS DMT (control), or discontinue their present DMT (experimental), in a 1:1 fashion using the Interactive Voice Response System (IVRS) randomization system. A total of up to 265 patients will be consented and enter the trial. After allowing for up to 15% dropout rate, we aim for 225 (112 in each group) patients to complete the study. Patients enrolled after July 31, 2019 will not complete the full two years of assessments; study follow up will only continue until September 1, 2021. There will be no placebo, and no sham treatment. There will be no taper period. (Please see the statistics sections for power analyses).

At each site, extensive chart review will be used to identify eligible patients. Patients will be approached at their next standard of care clinical visit by their primary neurologist and/or a study coordinator about participating in the study. Either the patient's primary neurologist or the study PI will verify inclusion/exclusion criteria and ensure that all patient's questions are answered before consent is signed. Study information may be distributed in the community in order to recruit participants from other sources. Patients who do not receive their standard neurological care at the study site will be encouraged to transfer their neurological care to the study site for the duration of the study. If this is not possible, these subjects must agree to have standard of care MRIs done by their primary neurologist yearly throughout the study and have the results sent to the study site. MRIs at the 6-month time point must be conducted at the study site. All research visits will be conducted at the same time as SOC visits when possible, or as separate visits if not possible.

Please see Table 1 below for the schedule of study activities.

Table 1: Schedule of Research Assessments

MS Patients consented for the study	T ₀ (Baseline)	T ₁ (6 Months +/- 1 week)	T ₂ (12 Months +/- 1 week)	T ₃ (18 Months +/- 1 week)	T ₄ (24 Months +/- 1 week)***	Unscheduled Visit*	Phone follow-up (monthly +/- 1 week)
Informed Consent	X	-	-	-	-	-	
Inclusion/Exclusion	X	-	-	-	-	-	
Physical Exam/ MS Medical History	X	-	-	-	-	-	
Vitals	X	X	X	X	X	X	
Prior/Con Meds	X	X	X	X	X	X	X
Adverse Events	X	X	X	X	X	X	X

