c. Aim #3: Proposed Data Analysis: Descriptive statistics on patient demographics, PDSS, MSIS, performance and NeuroQOL short form scales, and all other PROs will be prepared for treatment group by occurrence of disease event, and qualitatively compared. Pre-Post change will be compared between treatment groups. Change scores will be used for continuous and metric outcomes, and the treatment groups will be compared with two sample T-tests, or Wilcoxon tests if necessary. Binary outcomes, such as dichotomized changes in EDSS and other scales, will be tested with chi-square and proportion tests, or exact analogs if necessary. MSIS will be divided into patients with greater or less than a change of 7.5 (considered a significant change). Correlations between continuous scales will be examined, and compared between treatment groups. Events will also be compared to non-events, and combinations of (event outcome) will be tested for differences, using similar methods, in the unlikely situation there are enough events to permit meaningful statistical analysis (≥ 10 samples for an analysis group). Multiple groups can be tested with ANOVA methods for continuous outcomes, and with chi-square tests and logistic regression for binary outcomes.

Sample Size Estimation: Our null hypothesis for AIM #1, inferiority of the discontinue group, is a disease event proportion of 0.02 for the continue group, and 0.10 for the discontinue group. Our alternate hypothesis for the power calculation, non-inferiority of the discontinue group, is a disease event rate of 0.02 for both the continue and discontinue groups. Our study population consists of stable patients, so we expect the disease event rate to be very small for the continue group, and possibly the discontinue group as well. For a target alpha level of 0.025, a sample size of 112 per treatment group (225 total), would achieve 95% power for the non-inferiority test. For a single treatment group with 112 samples, if the true proportion is 0.02, then the upper bound of an exact confidence intervals can be expected to be less than 0.11 more than 95% of the time. Anticipating a dropout rate of approximately 9-15%, we plan to attempt to recruit 132 patients per treatment group (265 total).

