For secondary outcomes AIMS 2-3, a two sample t-test comparing change scores between treatment groups with an alpha level of 0.05 and an effect size equal to 38% of the standard deviation would achieve 80% power, and an effect size of 44% of the standard deviation would achieve 90% power. A two sample proportion difference test between treatment groups with an alpha level of 0.05 and an effect of approximately 0.19 would be able to achieve 80% power, and an effect of 0.22 would achieve 90% power. A relative risk test with an alpha level of 0.05, a control proportion of 0.3

or 0.5, and a ratio of 1.61 or 1.37 respectively would achieve 80% power, and a ratio of 1.71 or 1.42 respectively would achieve 90% power. A Pearson correlation of 0.27, within a group of 112 samples, between two normally distributed variables, would be detectable with 80% power for an alpha level of 0.05, and a Pearson correlation of 0.30 would be detectable with 90% power.

Table 2: Safety Comparisons of the two groups at 25 patients in each group

Sample per Group = 25		
Group	# of Events	Percent
Continue	0	0.00
Discontinue	7	28.00
Proportion		
Difference Estimate	95% Confidence Interval	
0.2800	0.1067	0.4939

Sample per Group = 25		
Group	# of Events	Percent
Continue	1	4.00
Discontinue	10	40.00
Proportion		
Difference Estimate	95% Confidence Interval	
0.3600	0.1311	0.5765

Table 3: Safety Comparisons of the two groups at 65 patients in each group

Sample per Group = 65		
Group	# of Events	Percent
Continue	1	1.54
Discontinue	15	23.08
Proportion		
Difference Estimate	95% Confidence Interval	
0.2154	0.1083	0.3407

Table 4: pValues in Dark Grey
denote statistically significant events
in discontinuers (vertical axis) vs
continuers (horizontal) at interim
analysis of 25 patients in each group.

Sample per Group = 25							
Null Hypothesis for p (Expected # of Events)							
# of Events	0.02 (0.5)	0.04 (1)	0.08 (2)	0.10 (2.5)	0.12 (3)	0.16 (4)	0.20 (5)
1	0.3965	0.6399	0.8756	0.9282	0.9598	0.9872	0.9962
2	0.0886	0.2642	0.6053	0.7288	0.8195	0.9263	0.9726
3	0.0132	0.0765	0.3232	0.4629	0.5912	0.7870	0.9018
4	0.0014	0.0165	0.1351	0.2364	0.3525	0.5837	0.7660
5	0.0001	0.0028	0.0451	0.0980	0.1734	0.3707	0.5793
6	0.0000	0.0004	0.0123	0.0334	0.0709	0.2002	0.3833
7	0.0000	0.0000	0.0028	0.0095	0.0243	0.0920	0.2200
8	0.0000	0.0000	0.0005	0.0023	0.0070	0.0361	0.1091
9	0.0000	0.0000	0.0001	0.0005	0.0017	0.0243	0.0468
10	0.0000	0.0000	0.0000	0.0001	0.0004	0.0035	0.0173

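### Aim 3 makes one no-worse claim on quality of life but compares about 17 scales with no lead outcome; a chance worsening on at least one is roughly 14% to 35% likely, against 2.5% for one scale

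*Combined protocol and SAP*

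**What the plan says.** Section I states one secondary hypothesis on patient-reported outcomes: "no worsening of patient quality of life as measured by a series of Patient Reported Outcomes (PROs), compared to those staying on their DMT". Aim 3 repeats it as one statement: "Quality of life and other patient-reported outcomes (PROs) are no worse in those discontinuing".

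Section III.A, Specific Aim 3, lists 13 Neuro-QoL item banks (2 physical, 2 symptom, 3 cognitive, 4 emotional, 2 social). It then adds SymptoMScreen, PDDS, SDMT and MSIS-29, making 17 scales. A treatment satisfaction question follows, which the plan itself calls qualitative and exploratory. For MSIS-29 the plan gives a reason: the Neuro-QoL short form cannot "provide an overall quality of life calculation, the study team added MSIS-29".

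Section III.F.c sets the comparison: "Change scores will be used for continuous and metric outcomes, and the treatment groups will be compared with two sample T-tests, or Wilcoxon tests if" (the last clause makes the Wilcoxon test a fallback). It also splits MSIS at a 7.5-point change, which it regards as significant, and so adds a binary test on the same scale. The power paragraph in III.F reads "For secondary outcomes AIMS 2-3, a two sample t-test comparing change scores between treatment groups with an alpha level of 0.05", and continues that "an effect size equal to 38% of the standard deviation would achieve 80% power, and an effect size of 44% of the standard deviation" gives 90%.

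The documents contain no lead scale, no hierarchy, no multiplicity adjustment and no joint decision rule for Aim 3. The exploratory label in the sample-size text applies to MS subtype and heterogeneity of treatment effect. It does not apply to Aim 3.

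**The concern.** One claim rests on many separate comparisons, and nothing says how they combine. If one Neuro-QoL domain is significantly worse after stopping and sixteen scales are not, the plan does not say whether the no-worse hypothesis has failed. The answer would be settled after the results are known.

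The plan treats the patient viewpoint as central to the decision to stop (section II) and expects patients, insurers and regulators to use the results (section III.G). Patients know their assignment, and III.E concedes that this may bias the patient-reported outcomes. A chance worsening on one scale would add to a comparison that is already hard to interpret.

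**Working it through.** 1. **Inputs.** Per-group size: "we aim for 225 (112 in each group) patients to complete the study". This is after dropout: "Anticipating a dropout rate of approximately 9-15%, we plan to attempt to recruit 132 patients per treatment group (265 total"), and 132 × 0.85 = 112.2. Alpha is 0.05 and sidedness is not stated. The count is 13 + 4 = 17 scales.

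2. **The plan's own power.** Normal approximation: power = Φ(d·√(n/2) − 1.96), with √(112/2) = 7.483.
   - d = 0.38: Φ(2.844 − 1.96) = 81.2% (80.8% with the noncentral t).
   - d = 0.44: Φ(3.293 − 1.96) = 90.9% (90.6%).

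   The stated 80% and 90% reproduce, so the 0.05 is two-sided and applies to one test. It is not divided across scales.

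3. **Which error counts.** Only a significant worsening contradicts a no-worse claim. For one scale under no true effect its chance is 0.05/2 = 2.5%.

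4. **At least one scale significantly worse, no true effect, 17 scales.** Independent: 1 − 0.975^17 = 35.0%. With a common correlation ρ between the test statistics: 1 − ∫ Φ((1.96 − √ρ·u)/√(1−ρ))^17 φ(u) du. The documents give no correlations, so ρ is assumed.

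| Assumed ρ | At least one scale worse | At least one significant, either direction |
|---|---|---|
| 0 | 35.0% | 58.2% |
| 0.3 | 25.4% | 49.3% |
| 0.5 | 19.4% | 38.6% |
| 0.7 | 13.5% | 27.1% |

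5. **Sensitivity to the count (independent scales, worse direction).** Adding the satisfaction item (18): 36.6%. Leaving out PDDS, which is also named as a control variable (16): 33.3%. Leaving out SDMT as well, as a performance test (15): 1 − 0.975^15 = 31.6%. The count hardly matters.

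6. **Two remedies compared.** One lead scale at two-sided 0.05 keeps the false-worsening chance at 2.5% and the power at 81% for 0.38 SD. Bonferroni over 17 scales (0.05/17 = 0.0029 each) cuts power to 45% at 0.38 SD. It raises the effect detectable with 80% power to 0.51 SD, and 202 per group would be needed to restore 80% at 0.38 SD.

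7. **Precision for an interval-based verdict.** The 95% interval extends about 1.96·√(2/112) = 0.26 SD either side of the estimate. If the arms are truly equal, the limit on the worse side excludes a margin of (1.96 + 0.842)·√(2/112) = 0.374 SD with 80% probability. A 7.5-point margin would therefore be met with at least 80% probability if the SD of MSIS-29 change is no more than about 7.5/0.374 = 20 points. The documents do not give that SD.

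**The case against.** The 0.05 is in a power statement and is not a decision rule. III.F.c also says the descriptive results will be compared qualitatively. This stands: a reader might infer that the plan commits to a pass-or-fail verdict on each scale at 0.05, and the documents do not say that. They do prescribe difference tests on change scores and give no other secondary alpha, so the open question of how to read 17 results remains.

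A reader might also take the either-direction figures, up to 58%, as the chance that the hypothesis is contradicted. The documents do not support that, because the claim is one-directional and an improvement does not contradict it. The 35% is an upper figure too. The scales overlap, with fatigue, cognition, mobility, depression and anxiety appearing in both Neuro-QoL and SymptoMScreen, so independence is implausible and the lower rows of the table are nearer the mark.

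On the choice of lead, the plan calls Neuro-QoL superior to existing MS-specific measures and wants a broad view of symptoms and trade-offs. That is a real cost of naming MSIS-29. It does not overturn the choice, since the plan itself says Neuro-QoL yields no overall score.

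Finally, if every scale had to clear its own non-inferiority margin, no alpha adjustment would be needed. That is correct, but the plan has no such rule and no margins.

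**Conclusion.** The point holds at modest severity. Aim 3 is one no-worse hypothesis with no rule linking it to about 17 comparisons. Under no true effect, the chance of at least one significant worsening is 35% if the scales are independent and about 14% to 25% for correlations of 0.7 down to 0.3. That is roughly 5 to 14 times the 2.5% for one scale. These figures assume two-sided tests at 0.05 on every scale, one pre-post comparison per scale and a common correlation. The extra MSIS split and any repeated visits are not counted.

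A second gap bears on the remedy. A non-significant difference test does not show no worse, so naming a lead scale while keeping only the t-test would still not answer the hypothesis.

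Nothing here touches the primary relapse-or-MRI analysis, and it should not be read as saying that the trial's main conclusion is at risk.

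**What to change.** In section III.F.c:

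- Name MSIS-29 change from baseline, at a stated visit, as the single lead outcome for the Aim 3 hypothesis. The plan already says it was added to supply the overall quality-of-life measure.
- Judge no worse from the 95% confidence interval of the between-group difference, against a margin stated in advance. The 7.5-point change already in III.F.c is one candidate. The plan uses it to classify individual patients, so its use as a between-group margin needs a sentence of justification.
- State that non-significance will not be read as no worse.
- Report the other scales as supportive estimates with 95% intervals and no hypothesis verdict.
- Record that the choice was made before any outcome data were seen by arm. This matters because the version dated 10 January 2020 provides for participants who finish before its approval, and treating physicians know the assignments.

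The cost is a short paragraph and that dated record, with no new patients, visits or data, and the stated power for the lead scale's t-test is unchanged. The downside is that an isolated change on one Neuro-QoL domain, from the system the plan rates more highly, becomes supportive only.
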